**The proposed specific aims are:**

**Specific Aim 1: To develop and refine a patient- and family-centered TBI transitional care intervention.**

The intervention will aim to improve functional status for patients with TBI, reduce strain for family caregivers, and direct patients and families to appropriate resources and care that is concordant with their health-related goals. We will use a combination of existing clinical guidelines, our prior and ongoing research, and a scoping review of care transitions literature to guide intervention development. We will create a manualized, intervention protocol that will undergo iterative user-testing with 6 focus groups (total 45-60 people) of patients with TBI, families, and healthcare providers to determine acceptability and to refine to ensure the intervention meets specific needs and preferences of patients with TBI and families.

**Specific Aim 2: To examine the feasibility and acceptability and assess the preliminary efficacy of the TBI transitional care intervention.**

The intervention will be tested with 15 dyads of patients with TBI discharged home from acute hospital care and their family caregivers. Recruitment, enrollment, data collection feasibility and intervention fidelity will be used to assess feasibility of implementation. We will develop a survey to assess acceptability. Preliminary efficacy will be estimated based on changes from baseline to intervention endpoint in the primary outcome of patient functional status at 8 weeks post-discharge (using Functional Status Examination). We will also examine secondary outcomes at 8 weeks post-discharge, including family caregiver strain and preparedness for the caregiving role and patient and family caregiver self-efficacy and healthcare utilization.

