## E. APPROACH

**Setting and Population.** All patients with TBI meeting inclusion criteria admitted to Duke University Hospital (DUH) neuro units 8W and 4100 and the 6 DUH medical-surgical/trauma units will be invited to participate in studies for aim 1 and 2. Collaborators on this award, [name], MD, neurologist and Vice Chair of Neurology Clinical Operations and [name], MD, trauma surgeon and Chief of Trauma and Critical Care Surgery, have agreed to facilitate recruitment from their respective areas (see letters of support).

**Inclusion Criteria.** Patients with TBI will be eligible if they meet the following requirements: a) age 18-64 years; b) diagnosed with moderate or severe TBI [admission Glasgow Coma Scale score of 3-12]; c) admitted to a DUH inpatient unit; d) plans to be discharged home from DUH; e) sufficient cognitive functioning to participate (i.e., able to follow 2-step commands), as determined by the Galveston Orientation and Amnesia Test (score  $\geq 76$  eligible); f) sufficient oral communication skills to participate, as determined by the Bedside Western Aphasia Battery-Revised (score  $\geq 93.8$  eligible); and g) English speaking (see Appendix A). [name] has successfully interviewed patients with TBI pre- and post-discharge with these criteria. Family members of patients with TBI will include biological relatives and friends and are eligible if they: a) are an anticipated primary caregiver after discharge (i.e., plans to live in same home as person or have direct contact with person  $\geq 10$  hours/week); b) age  $\geq 18$ ; and c) English speaking. Healthcare providers will be eligible if they: a) self-identify as a licensed provider and b) provide care to patients with TBI during the transition home (in hospital or within 8 weeks of discharge). All participants must be able to consent to participate.

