selected components for our intervention (based on our prior/ongoing research). It is important to note that, to date, clinical guidelines and research (such as that of the NICE guidelines and Transition of Care Taxonomy) address system structural components and processes but does little to explore behavioral mechanisms that empower families and patients to follow-through with training and treatment plans. Drawing on [name] (co-investigator) expertise in behavioral modifications, the intervention we develop will incorporate behavioral change mechanisms to increase the likelihood that patients and families follow-through with training and treatment plans. The intervention's key processes will aim to improve patient functional status, caregiver strain, and to direct patients and families to appropriate resources and care that is concordant with their health-related goals. We will create a manualized, intervention protocol, which will take 3 months.

**Refining the Intervention (Aim 1).** The manualized intervention protocol will undergo iterative user-testing to determine acceptability.

The 6 focus groups (6-10 participants each) will use a stratified, purposive sample to obtain informational representation. Focus groups will be organized concordantly based on insurance status and group membership (patient, family, or healthcare provider). We will have one group with patients with TBI and family members with insurance and one group without; one group with

Table 3. Transition of Care Taxonomy (TCT) Domains and Intervention Components	
TCT Domain	Pre-selected Components
Transition Type	Acute hospital to home
Model Type	Hospital-initiated
Recipient(s)	Patient and family caregiver
Key Transitional Care Processes	Assessment of needs, patient/family education, goal setting, care coordination, referral to resources, and individualized care plan
Intervention Facilitators	Multi-disciplinary team (e.g., nurse, case manager/social worker, therapists, mental health counselor)
Contact Method	In-person home visit, clinic visit, and phone calls
Intensity and Complexity	In-person home visit 7 days post-discharge, weekly calls, and comprehensive clinic visit at 2 weeks post-discharge
Outcomes	Patient, proxy-, and family-reported outcomes (see Aim 1 and 2)

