**Aim 2 Study Overview.** A research assistant will recruit, consent, and enroll 15 dyads of patients with TBI set to be discharged home from Duke University Hospital and their families to determine feasibility, acceptability, and preliminary efficacy of the TBI transitional care intervention. The intervention will be delivered by a multi-disciplinary team. Data will be collected at baseline (discharge), intervention midpoint (4 weeks post-discharge) and intervention endpoint (8 weeks post-discharge). The research assistant will assist with recruitment, consent, enrollment, and data collection. Assessing the feasibility, acceptability, and preliminary efficacy of the intervention will take 15 months.

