**Aim 2 Analysis Plan.** All statistical analyses will be conducted by [name] who is co-investigator on this award and a statistician. We will use descriptive statistics to assess all feasibility data. Preliminary efficacy will be evaluated based on changes from baseline to intervention endpoint for primary and secondary outcomes. We will estimate the variance of the change in all outcomes and estimate the effect size of the intervention using Cohen's D. We will estimate missing data and dropout rate at each time point based on these preliminary data. Combined with our clinical judgements, this information will provide important insights in proposing a clinical meaningful effect size to guide sample size calculation for our future R01 where we will conduct a full scale intervention RCT to formally establish the intervention effectiveness.

**Potential Problems and Solutions.** We recognize some patients with TBI may not have sufficient cognitive functioning at the time of discharge or within 8 weeks post-discharge. Thus, we have built in multiple opportunities to collect data from family caregivers of patients with TBI in Aim 1 and 2 to ensure we have collected, at the very least, family members' perspectives to inform intervention development and refinement (Aim 1) and assessment of the feasibility, acceptability, and preliminary efficacy of the intervention (Aim 2).

**Timeline and Milestones (Table 4).** Prior to beginning this award, we will obtain IRB approval and hire and train study staff. We will complete Aim 1 by third-quarter year 1 and Aim 2 by end-year 2.

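### Patient health service utilization: the change from an in-hospital baseline to 8 weeks is not like-for-like, so its Cohen's d should not be labelled an intervention effect size

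*Combined protocol and SAP*

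**What the plan says.** The Aim 2 Analysis Plan (section E, Approach) sets one rule for every outcome: "Preliminary efficacy will be evaluated based on changes from baseline to intervention endpoint for primary and secondary outcomes". It continues: "We will estimate the variance of the change in all outcomes and estimate the effect size of the intervention using" Cohen's d. No outcome is exempted.

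The Aim 2 data collection section lists health service utilization, measured with a named inventory, as a secondary outcome for patients as well as caregivers. It also says that patients' baseline data are gathered face to face in the 48 hours leading up to discharge. The Inclusion Criteria require each patient to be "c) admitted to a DUH inpatient unit". The schedule in the Aim 2 Study Overview is: "Data will be collected at baseline (discharge), intervention midpoint (4 weeks post-discharge) and intervention endpoint (8 weeks post-discharge").

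Table 3 pre-selects these contacts as part of the intervention: "In-person home visit 7 days post-discharge, weekly calls, and comprehensive clinic visit at 2 weeks post-discharge". The documents do not state the inventory's look-back period or its unit (visits, days or cost). They do not say whether the index stay counts, or whether the intervention's own contacts count.

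Specific Aim 2 describes preliminary efficacy through "changes from baseline to intervention endpoint in the primary outcome of patient functional status", and then says "We will also examine secondary outcomes at 8 weeks post-discharge, including family caregiver strain" and other outcomes, healthcare utilization among them.

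**The concern.** A utilization count needs a period of time. For a patient assessed in hospital just before discharge, that period takes in the admission that made the patient eligible, life before the injury, or both. The follow-up period is 8 weeks at home after a moderate-to-severe brain injury. The two ends of the change score therefore measure different things.

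If the index stay is counted, every patient starts with at least one admission. Mean admissions then fall whenever post-discharge admissions average below one per patient, whatever the intervention does. If the window is pre-injury, use will tend to rise because the patient has since been injured. Outpatient contacts may rise further because the intervention itself supplies a home visit, a clinic visit and calls.

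What is at stake is interpretation. A d labelled as the intervention's effect size could look like a large benefit or a harm purely through the choice of window and unit. The same section lists effect-size information among the inputs, alongside clinical judgement, to an effect size for the later R01.

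**Working it through.** **Figure to reproduce.** There is none. The plan gives no utilization rate, SD or target effect for this outcome. The check is whether d stays near zero when the intervention does nothing.

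**Inputs from the documents.** Baseline is in hospital and the endpoint is 8 weeks after discharge. The target is 15 completing dyads from 20 enrolled, with 33% attrition expected (Sample Size Justification).

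**Assumed inputs, because the documents give none.**
- 8-week readmission risk r = 0.10 to 0.30.
- Pre-injury admission risk p = 0.01 to 0.05 (0.02 for the days calculation).
- Mean index stay m = 4, 7 or 14 days.
- At most one admission per window, windows independent, intervention effect zero.

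Throughout, d = mean change / SD of change, since the plan estimates the variance of the change.

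**1. Index stay counted, admissions coded 0/1.** Baseline is 1 for everyone.
d = -(1 - r) / sqrt(r(1 - r))
- r = 0.10: -0.90 / 0.300 = -3.00
- r = 0.30: -0.70 / 0.458 = -1.53

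**2. Index stay plus pre-injury time, admissions.**
d = (r - 1 - p) / sqrt(p(1 - p) + r(1 - r))
- p = 0.01, r = 0.10: -0.91 / 0.316 = -2.88
- p = 0.05, r = 0.30: -0.75 / 0.507 = -1.48

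**3. Index stay counted, inpatient days.** Take the index stay as 2 days plus an exponential with mean m - 2, so its mean is m and its variance (m - 2)². Take a readmission as 1 day plus an exponential with mean 4. Follow-up days then have mean 5r and variance 41r - 25r².
d = (5r - m) / sqrt((m - 2)² + 41r - 25r²)
- m = 4, r = 0.10: -3.5 / sqrt(4 + 3.85) = -3.5 / 2.80 = -1.25
- m = 4, r = 0.30: -2.5 / sqrt(4 + 10.05) = -2.5 / 3.75 = -0.67
- All nine combinations of m = 4, 7, 14 and r = 0.10, 0.20, 0.30 lie between these two values.

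**4. Pre-injury window only, admissions.**
d = (r - p) / sqrt(p(1 - p) + r(1 - r))
- p = 0.05, r = 0.10: 0.05 / 0.371 = +0.13
- p = 0.01, r = 0.30: 0.29 / 0.469 = +0.62

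**5. Pre-injury window only, inpatient days (p = 0.02).** Baseline mean is 5 × 0.02 = 0.10 and variance 41 × 0.02 - 25 × 0.02² = 0.81.
- r = 0.10: 0.40 / sqrt(0.81 + 3.85) = 0.40 / 2.16 = +0.19
- r = 0.30: 1.40 / sqrt(0.81 + 10.05) = 1.40 / 3.30 = +0.42

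**Reading.** With the intervention effect fixed at zero, moving the window from index stay to pre-injury reverses the sign. Changing the unit from days to 0/1 admissions moves the index-stay range from (-1.25, -0.67) to (-3.00, -1.53), and the two ranges do not overlap.

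**Precision of a descriptive alternative.** Exact (Clopper-Pearson) 95% intervals: 3 of 15 = 20% (4.3% to 48.1%); 0 of 15 = 0% (0% to 21.8%). Twenty dyads at 33% attrition leave 20 × 0.67 = 13.4, so about 13 patients may be nearer the mark: 3 of 13 = 23% (5.0% to 53.8%).

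**The case against.** **The baseline procedure is inferred.** No section says outright that the inventory is given to patients before discharge, and the cited inventory may define its own look-back. This stands as a limit. But the plan's rule needs a baseline value for every outcome. If one is collected, every available look-back has the problem; if none is collected, the change score cannot be computed. An exemption is needed either way.

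**A pre-injury window leaves only the usual single-arm limitation.** This is partly right: without a control group, no pre/post d isolates the intervention. Yet the other patient outcomes are scheduled after the injury at both times, whereas a pre-injury utilization count puts the injury itself into the contrast. That is an added and avoidable fault.

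**The size is unstable.** This stands. Every rate is assumed, and the values near -3 depend on coding admissions 0/1 with baseline fixed at 1. They should not be quoted as the expected bias.

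**Stronger readings that the documents do not support.**
- A reader might infer that Specific Aim 2 contradicts the analysis plan by examining secondary outcomes at 8 weeks. It uses the same time point for the primary outcome, which is a change score. It does not require a change score for secondary outcomes, but it does not exclude one.
- A reader might infer that the utilization d will size the R01. The plan says only that the pilot information, combined with clinical judgement, gives insight into a meaningful effect size.
- A reader might extend the point to caregiver strain, because a caregiver is eligible if they "are an anticipated primary caregiver after discharge". Any resulting bias cannot be sized or signed from the documents, and it belongs to the general single-arm limitation.

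**Conclusion.** The concern holds for patient health service utilization and is minor. Applied as written, the rule produces a d whose sign and size are driven by the look-back and the unit, neither of which the documents state. With zero intervention effect and assumed 8-week readmission of 10-30%, d is about -0.7 to -1.3 (inpatient days, mean stays of 4-14 days) or -1.5 to -3.0 (0/1 admissions) if the index stay counts. It is about +0.1 to +0.6 with a pre-injury window. The direction of the index-stay result needs only that post-discharge use be lower than the index admission. The magnitudes rest wholly on the assumed rates.

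The consequence is a risk of misreading. Utilization is secondary, functional status is the single primary outcome, the pilot is small, and formal effectiveness is left to a later randomized trial.

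**What to change.** In the Aim 2 Analysis Plan, exempt patient health service utilization from the change score and from Cohen's d. In their place:

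- Collect utilization at the planned 4- and 8-week calls, with recall covering weeks 0-4 and 4-8 after discharge, and exclude the index stay.
- Report use over the 8 weeks by service type, as proportions or rates with 95% confidence intervals.
- Show contacts delivered by the intervention (the Table 3 visits and calls, as finally adopted) separately from other care, using the record of delivered components already planned for fidelity.
- State that this summary is descriptive, does not isolate an intervention effect, and that no utilization d informs the R01 effect size.

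The cost is analysis-plan wording and a defined recall period at calls already scheduled, with no added visits or participants. The team should check that the cited inventory can be used with that recall period. The downside is that utilization will have no single standardized effect, and estimates from about 13 to 15 patients will be imprecise, as the intervals in the working show.

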**Aim 2 Data Collection for Feasibility, Acceptability, and Preliminary Efficacy.** Recruitment, enrollment, and data collection feasibility and intervention fidelity will be used to assess feasibility of implementation of the TBI transitional care intervention. For recruitment feasibility, the research assistant will record the number of patients and family caregivers eligible vs. number of patients and families consented to participate. For enrollment feasibility, the research assistant will record the number of patients and family caregivers eligible, consented, and enrolled into the intervention. For data collection feasibility, the research assistant will obtain in-person baseline data from patients with TBI up to 48 hours before discharge and will also obtain baseline data from family caregivers in person or by phone depending on availability. At 4- and 8-weeks post-discharge, the research assistant will call patients and families to obtain follow-up data. The research assistant will record for each follow up time point: 1) number of patients and family members called and reached; 2) number of call attempts per patient and family member; 3) number of patients and family members reached but unable to provide information; 4) completeness of data collected; 5) length of phone call; and 6) day of week and time of day patients and family members participated. Fidelity will be assessed by recording all components of the intervention delivered to each patient and family caregiver. Our team will review recruitment and follow-up rates weekly and identify strategies to improve recruitment, enrollment, and data collection. We will assess acceptability of the intervention using a survey we develop. The outcome data we collect will be used to assess preliminary efficacy. To assess the preliminary efficacy of the intervention, we will collect data on our primary outcome [patient functional status (Functional Status Examination)]. Secondary outcomes for family caregivers will include caregiver strain (Modified Caregiver Strain Index) and preparedness for the caregiver role (Preparedness for Caregiving Scale); secondary outcomes for patients and family caregivers will include self-efficacy (Self-Efficacy for Management of Chronic Conditions) and health service utilization (Health Service Utilization Inventory).

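### The one-group change from baseline to 8 weeks is labelled an intervention effect and helps set the future RCT's effect size, but it cannot be separated from change without treatment

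*Combined protocol and SAP*

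**What the plan says.** Specific Aim 2 describes one treated group: "The intervention will be tested with 15 dyads of patients with TBI discharged home from acute hospital care and their family caregivers". The Aim 2 Study Overview repeats this and mentions no control, historical comparison or randomisation. It places data collection at discharge, 4 weeks and 8 weeks.

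The efficacy contrast is within-group. Specific Aim 2 states: "Preliminary efficacy will be estimated based on changes from baseline to intervention endpoint in the primary outcome of patient functional status". The Aim 2 Analysis Plan extends this to every outcome: "Preliminary efficacy will be evaluated based on changes from baseline to intervention endpoint for primary and secondary outcomes". It continues: "We will estimate the variance of the change in all outcomes and estimate the effect size of the intervention using" Cohen's d. The SD that forms the denominator is not named.

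The intended use follows in the same section: "Combined with our clinical judgements, this information will provide important insights in proposing a clinical meaningful effect size to guide sample size calculation" for the planned R01, described there as a full-scale RCT.

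Under Aim 2 Data Collection, the research assistant "will obtain in-person baseline data from patients with TBI up to 48 hours before discharge", and at 4 and 8 weeks "the research assistant will call patients and families to obtain follow-up data".

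**The concern.** Without a comparator, the mean change from discharge to 8 weeks equals the intervention effect only if the outcome would otherwise have stayed flat. The plan neither states nor defends that assumption. For patients, the setting (hospital to home) and the mode of assessment (in person to telephone) also change over the same interval as treatment.

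The label matters because of the declared use. An RCT is powered on a difference between arms. If patients' functional status improves without the intervention, relying on this d would make the future trial too small. For other outcomes the error could go the other way: if caregiver strain rises untreated after discharge, d would understate the benefit and the trial could be larger than necessary. The Significance section itself faults earlier transitional-care research in TBI for insufficient power.

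**Working it through.** **What the documents supply.** They give one treated group, a baseline-to-8-week contrast, Cohen's d as the metric, and an RCT as the future design. They give no expected d, no estimate of untreated change, no alpha or power for the future trial, and no rule for turning d into a sample size. There is therefore no figure of the plan's own to reproduce on this point.

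**Can the design identify the effect?** Write the expected change in the treated group as C = T + U, where T is the intervention effect and U is the change that would have occurred without it, including any effect of setting or mode. One group estimates C only. The 4-week measurement falls after the intervention has begun, so it gives no untreated trend from which to estimate U.

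**Can U be taken as zero?** The inclusion criteria require an admission Glasgow Coma Scale score of 3–12, yet at enrolment a Galveston Orientation and Amnesia Test score of at least 76. Marked improvement before the intervention is built into eligibility. This does not quantify change after discharge, but a flat course cannot be presumed.

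**Size if d is used as the RCT effect.** My assumptions are two-sided 5%, 80% power, 1:1 allocation, a two-sample t-test (noncentral t), and the same SD for the pre-post d and the RCT d. If a share s of the pre-post d is untreated change, the between-arm effect is d × (1 − s).

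| Pre-post d | Sized at, per arm | Needed if s = 25% | s = 50% | s = 75% |
|---|---|---|---|---|
| 0.5 | 64 | 113 (d 0.375) | 253 (d 0.25) | 1006 (d 0.125) |
| 0.8 | 26 | 45 (d 0.6) | 100 (d 0.4) | 394 (d 0.2) |
| 1.0 | 17 | 29 (d 0.75) | 64 (d 0.5) | 253 (d 0.25) |

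In each row the power of the trial as sized falls from about 80–81% (s = 0) to about 56%, 29% and 11%. As a hand check, the normal approximation n = 2(1.96 + 0.84)²/d² gives 2 × 7.84/0.64 = 24.5, or 25 per arm, at d = 0.8. The t-based figure is one higher.

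**Opposite direction.** If an outcome improves by 0.4 SD under treatment but would have worsened by 0.2 SD without it, the true difference is 0.4 + 0.2 = 0.6 SD. Sizing on 0.4 gives 100 per arm when 45 are needed.

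**No intervention effect at all.** With 15 completers and an untreated change of 0.3, 0.5 or 0.8 SDs of change, simulation gives a mean d of 0.32, 0.53 or 0.85. The chance of observing d ≥ 0.5 is 24%, 51% or 87%.

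**Precision.** Taking the SD of change as denominator and n = 15, an observed d of 0.5 has a 95% CI of −0.05 to 1.03, and an observed 0.8 has 0.20 to 1.37.

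**Unnamed denominator.** With equal SDs at both times and correlation r between them, d on the SD of change = d on the baseline SD / √(2(1 − r)). A change of 0.8 baseline SDs becomes:
- r = 0.3: 0.8/√1.4 = 0.68
- r = 0.5: 0.8/√1.0 = 0.80
- r = 0.7: 0.8/√0.6 = 1.03
- r = 0.8: 0.8/√0.4 = 1.26

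**The case against.** The plan is already cautious. It calls the efficacy preliminary, plans no hypothesis test, leaves effectiveness to the RCT, and combines the pilot information with clinical judgement. It never says that d will be the R01 effect size. Any harm would arise in a later document, and the sample-size illustration rests almost wholly on assumed values. The plan describes usual care as ineffective for functional outcomes, which might suggest little untreated change. The in-person-to-telephone shift is fixed only for patients, since caregiver baselines may be taken by telephone. Mentioning the variance of change beside Cohen's d hints at the SD of change as denominator. Finally, disowning d as an effect estimate leaves the preliminary-efficacy aim without an estimator.

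Much of this limits the size of the point: the magnitude is illustrative, its direction depends on the outcome, and the mode argument applies fully only to patients. It does not remove the defect. Calling a result preliminary signals imprecision, not confounding with time. Clinical judgement is invoked, but nothing tells the reader that d is uncontrolled, and the Potential Problems section covers only cognitive functioning. The statement about usual care does not show that patients remain unchanged between discharge and 8 weeks. A hint about the denominator is not a definition. Within-group change can still be reported under the aim; what must go is the claim that it measures the intervention's effect.

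**Conclusion.** The point stands: the plan is wrong as written and should be corrected. It attributes to the intervention a quantity that a one-group design cannot attribute, and it names the sizing of an RCT as a use. That conclusion follows from the design and needs no numerical assumption.

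The consequence for the R01 does rest on assumptions. It depends on how far d is relied upon and on an untreated share that the documents do not give. Across shares of 25% to 75%, a trial sized on d alone would have roughly 56% down to 11% power instead of 80%. Where an outcome would worsen untreated, the trial would be oversized instead. The feasibility and acceptability results, and the pilot's estimates of variance and dropout, are unaffected.

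**What to change.** 1. In the Aim 2 Analysis Plan, replace the phrase that attributes the effect size to the intervention with: mean within-participant change from baseline to 8 weeks, standardised by a stated SD, with 95% CI; uncontrolled and not an estimate of intervention effect. Name the SD (baseline or change). Align the wording of Specific Aim 2.
2. State that this d will not serve as the R01 effect size, which will be set from a clinically meaningful between-group difference.
3. State that the pilot will supply the SDs, the baseline-to-8-week correlation, missing data and dropout, each with a confidence interval.

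The cost is a few sentences, plus an editorial pass over the other mentions of preliminary efficacy so that they agree. No participants, visits or data are added. The price is a less favourable efficacy statement and possibly a larger planned R01.
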